6.3.3 Efficacy Analysis

This initial clinical study using the Anterior Vertebral Tether Device for pediatric idiopathic scoliosis is focused on safety and feasibility, not efficacy, as primary endpoints. There will be an exploratory therapeutic endpoint, Cobb angle change, based on an intention to treat approach and will include all subjects who have undergone the intervention.

The exploratory therapeutic endpoint used for efficacy will be change in post-operative Cobb angle compared to pre-operative Cobb angle, measured on coronal radiograph of the spine. Considering change in Cobb angle is a continuous variable, a t-test will be used to detect any change in Cobb angle post-operatively. Linear regression will be utilized to assess which variables are associated with change in post-operative Cobb angle.

6.3.4 Live Case Demonstration Analysis

Data collected from the subject participating in the live case demonstration will be stratified from the rest of the subjects during analysis. A comparative analysis will be performed to determine whether there are significant differences in risks and outcomes between the live case subject and subjects who were not involved in a live case presentation. If such differences exist, the data from the live case presentation will be excluded from efficacy analyses and independently analyzed. Exclusion of the live case subject from analyses will not impact the power calculations described in Section 6.4.

6.4 Sample Size and Power

The purpose of this study is to longitudinally follow a cohort of patients treated with a novel use of an implanted device, referred to as the Anterior Vertebral Tether Device, to explore safety and feasibility of the implant. Based on device implantation in up to 40 subjects, the study will not be sufficiently powered to gain statistical significance. However, this preliminary study will allow some insight into the safety of implantation, as measured by the acceptability of adverse events, as well as feasibility of implantation, as estimated by the proportion of successful implants of the Anterior Vertebral Tether Device. The regulatory status of such an implant requires that the Sponsor obtains an IDE. There is no active comparative group in this limited study. Notably, there is a useful comparator group from review of published data (historical controls) and from the data of the Harms Study Group (CHOP IRB# 06-005052), for which the Sponsor has access. A comparative analysis will be performed combining data from this clinical trial with IRB# 06-005052 to evaluate patient factors and clinical outcomes depending on the intervention received. Data from this clinical trial will not be shared with IRB# 06-005052.

Using data observing pre and post thoracic and lumbar measurements for a small sample of subjects; for the thoracic measurements, a sample size of 40 will have >80% power to detect a difference in means of 17.9, assuming a standard deviation of differences of 6.6, using a paired t-test with a 5% two-sided significance level. For the lumbar measurements, a sample size of 40 will have >80% power to detect a difference in means of 6.5, assuming a standard deviation of differences of 5.38, using a paired t-test with a 5% two-sided significance level. Sample size calculations were performed using NQuery software.

6.5 Interim Analysis

The study team will perform interim analyses based on the stopping rules listed in section 6.6 (below). If any of these rules are met, the study will halt enrollment until appropriate measures can be put in place to reduce patient risk. All reporting of AEs/SAEs during the study will adhere to the guidelines in Section 8 (Safety Management).

6.6 Stopping Rules

The stopping rules for this study will be based on the prevalence of SAEs. There is special consideration given to SAEs that are found to be “device-related”, as outlined below.

6.6.1 Stopping rules for any SAE related to the study procedure (surgery)

- SAE in all of the first 5 patients or
- SAE in 7 of first 10 patients or
- SAE in greater than 50% of patients after 15 cases

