8.4 Definition of a Serious Adverse Event (SAE)

An SAE is any adverse event that results in any of the following outcomes:

- death,
- a life-threatening event (at risk of death at the time of the event),
- requires inpatient hospitalization or prolongation of existing hospitalization,
- a persistent or significant disability/incapacity, or
- a congenital anomaly/birth defect in the offspring of a subject.

Important medical events that may not result in death, be life-threatening, or require hospitalization may be considered a serious adverse event when, based upon appropriate medical judgment, they may jeopardize the subject and may require medical or surgical intervention to prevent one of the outcomes listed in this definition.

A distinction should be drawn between serious and severe AEs. A severe AE is a major event of its type. A severe AE does not necessarily need to be considered serious. For example, nausea which persists for several hours may be considered severe nausea, but

would not be considered serious. On the other hand, a stroke that results in only a limited degree of disability may be considered a mild stroke, but would be considered serious.

We will use the Clavien-Dindo Classification system [47], as well as the Comprehensive Complication Index (based off of the Clavien-Dindo system) [48] to classify and analyze patient adverse events. **Grade III (a/b), Grade IV (a/b), and Grade V events will be considered SAEs. (See Appendix 1 for classification table)**

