9.3 Regulatory and Ethical Considerations

9.3.1 Data and Safety Monitoring Plan

The PI will monitor data and safety throughout the duration of the study and will report any adverse events in accordance with IRB policies. The PI, Safety Monitor, and study team will

perform interim safety analyses as outlined in Section 6.6. Safety monitoring will be handled internally by the study Safety Monitor and CHOP Office of Research Compliance (ORC). We will also submit reports to the FDA, device manufacturer, or both as per medical device reporting requirements specified in 21CFR803.

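### No halt rule in Section 6.6 takes account of severity: procedure-related deaths in 4 of the first 5 children would meet no pre-specified limit for pausing enrolment

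*Combined protocol and SAP*

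**What the plan says.** Section 6.6 states the basis of stopping: "The stopping rules for this study will be based on the prevalence of SAEs". It draws one distinction among SAEs: "There is special consideration given to SAEs that are found to be “device-related”, as outlined below".

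For SAEs related to the surgery, Section 6.6.1 gives three limits: "SAE in all of the first 5 patients", "SAE in 7 of first 10 patients", or "SAE in greater than 50% of patients after 15 cases". For device-related SAEs, Section 6.6.2 gives lower early limits (3 of the first 5, 5 of the first 10, more than 50% from case 15). These apply separately to three defined events: screw, locking cap or staple failure; tether failure; and implant re-operation.

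Section 6.5 gives the consequence: "If any of these rules are met, the study will halt enrollment until appropriate measures can be put in place to reduce patient risk". Section 9.3.1 refers back to the same rules: the PI, Safety Monitor and study team will "perform interim safety analyses as outlined in Section 6.6".

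Section 8.4 defines what is counted. Besides the usual outcome criteria, it says "Grade III (a/b), Grade IV (a/b), and Grade V events will be considered SAEs". By Appendix 1, that range runs from a procedure done without general anaesthesia (IIIa) to death (V).

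Outside the stopping rules, Section 8.4.1 has the PI and Safety Officer judge the relationship of every SAE case by case. Section 8.6 requires notice to the IRB within 24 hours of a death or life-threatening SAE, and a written report within 2 calendar days.

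**The concern.** High limits can be defended for Grade III events, some of which are to be expected after thoracoscopic spine surgery and can be managed. The same limits apply to death and to permanent neurological injury, where a single event could change the risk-benefit conclusion in Section 9.3.4. As written, five children who each need a minor procedure without general anaesthesia would halt enrolment. Four deaths and one uneventful case would not.

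Section 6.3.3 describes this as the initial clinical study of the device for this indication. The subjects are aged 8 to 16 and safety is the primary endpoint. Section 9.3.2.1 names neurological injury as a risk, and the synopsis lists neuromonitoring events among the safety evaluations, yet no halt rule uses either. The purpose of a pre-specified rule is that a pause after a grave event should not depend on discretion. That matters more in a single-site, sponsor-investigator trial whose safety monitoring is handled internally (9.3.1).

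**Working it through.** The documents give no expected or tolerable SAE rate and no halt probability, so there is no stated figure to reproduce. The rules can be applied directly.

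**Inputs.** Limits from 6.6.1 and 6.6.2; SAE grades from 8.4 and Appendix 1; up to 40 subjects (6.4); 5-10 subjects a year (3.3.2).

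**Step 1: four deaths in the first five children.** Suppose each is procedure-related, none involves an implant re-operation or a defined implant failure, and the fifth child has no procedure-related SAE.
- First limit: 4 < 5, not met.
- Second limit: 4 < 7, not met.
- The 50% limit is not yet active.
- The limits in 6.6.2 are not met, because none of the events is of a type counted there.

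**Step 2: largest number of such events that meets no rule.**
- First 5: 5 − 1 = 4.
- First 10: 7 − 1 = 6.
- First 14: 6 + 4 = 10, because no rule covers cases 11 to 14.
- First 15: 7, since 8/15 exceeds 50%, if the third limit applies at case 15. If it starts at case 16, 6 + 5 = 11 would pass at case 15.
- First 40: 20, since 20/40 does not exceed 50%.

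**Step 3: how the 6.6.1 limits respond.** The event rates here are assumptions chosen to show the shape of the rule, not forecasts. At 10%, the chance of 5 of 5 is 0.1^5 = 0.00001, and the chance of at least 7 of 10 is 0.000009. An exact case-by-case recursion over 40 cases, reading the third limit as active at every case from 15 on, gives:

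| Assumed rate of counted events | Halt within 10 cases | Halt within 40 cases |
|---|---|---|
| 10% | below 0.01% | 0.01% |
| 20% | 0.1% | 0.6% |
| 30% | 1.2% | 7.3% |
| 40% | 5.8% | 33% |
| 50% | 17.8% | 73% |

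The rate is that of all counted SAEs. Less severe SAEs in other children would bring a halt nearer, but severity itself contributes nothing.

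**Step 4: how often a single-event hold would occur.** The chance of at least one event in 40 subjects is 1 − (1 − p)^40:
- p = 0.1%: 1 − 0.999^40 = 3.9%
- p = 0.5%: 1 − 0.995^40 = 18.2%
- p = 1%: 1 − 0.99^40 = 33.1%

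For an assumed hold of one to two months, enrolments deferred run from 5/12 × 1 = 0.4 to 10/12 × 2 = 1.7.

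**The case against.** **A reader might infer that further children would be operated on before any required review.** The documents do not support that. Case-by-case determination (8.4.1) and IRB notice of a death within 24 hours (8.6) are both required. At 5-10 enrolments a year, surgeries average about 365/10 = 36.5 to 365/5 = 73 days apart, so at average spacing these steps come before the next operation. What the plan lacks is a stated hold, not a review.

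**A reader might infer that enrolment must continue below the limits, or that these rules are the only way to halt.** Section 6.5 says what happens when a rule is met; it does not oblige enrolment to go on otherwise. Sections 8.7 and 8.8 provide for withdrawal of IRB approval, and 8.8 for withdrawal of FDA approval, and the sponsor could act on its own. Referenced IRB procedures or conditions attached to the IDE might also impose a hold; that cannot be checked here. The claim is limited to what the protocol states.

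**A reader might infer that every paralysis escapes the device limits.** A neurological injury that was an implant problem requiring re-operation (removal, loosening of tension or fusion) would count under 6.6.2, where 3 of 5 halts enrolment. Other neurological injuries, and deaths without such a re-operation, would not. Nor are all SAEs treated alike in every respect: device-related events have their own limits. The gap is in severity.

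**Four deaths in five is an extreme case, and Section 9.3.2.1 reports no known adverse neuromonitoring events with this surgery.** Both points are fair. The extreme case shows only where the limit sits. The practical gap is that a first or second death triggers no stated pause.

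**Conclusion.** The point stands in a limited form: no halt rule in Section 6.6 depends on severity, and the protocol states no enrolment hold after a death or a disabling neurological injury. The counts of 4 of 5, 6 of 10 and 10 of 14 follow directly from the limits, provided that the remaining children have no procedure-related SAE and that the events are not of a type counted in 6.6.2. The count at case 15 depends on how the third limit is read. The halt probabilities rest on assumed rates and are illustrations only.

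No passages contradict each other and no stated figure is wrong. This is a design choice that can be improved at little cost, so the change is a cheap improvement rather than the correction of an error.

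**What to change.** Leave the limits in 6.6.1 and 6.6.2 unchanged for all SAEs. Grade IV must stay in the existing count; confining those limits to Grade III would weaken the present rule.

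Add to 6.6 a hold on enrolment of further subjects, pending Safety Officer and IRB review, after any single:
- Grade V event, or
- neurological deficit that meets the disability criterion of Section 8.4,

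judged at least possibly related to the procedure or the device. Cross-reference the hold in 6.5 and 9.3.1. Tying the neurological trigger to the 8.4 criterion avoids a new definition. Grade and relatedness are already assessed under 8.4 and 8.4.1, so no new data are needed.

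The cost is a short addition to 6.6, two cross-references and a possible brief pause, with the chance and length set out in the working. The change concerns enrolment only, not the care of subjects already treated.

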6.6.2 Stopping rules for SAEs that are device-related

Definition of Terms:

- Screw failure – screw, locking caps, and/or centering staple have loosened from the vertebra AND require re-operation.
- Tether failure – the tether has broken or lost tension. Diagnosed at any time point after 3 months by increased angulation at a disc space on standing PA radiograph or increase in disc wedging on side bending x-ray to the side away from the implant. Also, it is only an SAE if noted before maturity, overall Cobb angle worsens compared to the first erect measurement, AND requires re-operation.
- Implant re-operation - any problem with the implant that requires re-operation including re-operation for overcorrection with any of the following: a removal of all or part of the implant, loosening of the tension on the implant, or spinal fusion.

Stopping Rules

- Screw/locking cap/staple failure stopping point: 3 of first 5 cases, 5 of first 10, or in greater than 50% of cases 15 and beyond.
- Tether failure stopping point: 3 of first 5 cases, 5 of first 10, or greater than 50% of cases 15 and beyond.
- Implant failure re-operation stopping point: occurs in 3 of first 5, 5 of first 10, or greater than 50% of cases 15 and beyond.

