3.3.2 Total Number of Study Sites/Total Number of Subjects Projected

The study will be conducted at The Children's Hospital of Philadelphia.

This study is a clinical investigation of the anterior vertebral tethering procedure in up to 40 subjects using the investigational device elements as described within this protocol. Based on a broad review of patient visits over the past year, we may expect to enroll about 5-10 patients per year.

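### The late tether-failure limit sets no follow-up condition, so during accrual the monitored rate is biased low and toward not halting; how much depends on failure timing that the plan does not give

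*Combined protocol and SAP*

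**What the plan says.** Section 6.6 states the measure: "The stopping rules for this study will be based on the prevalence of SAEs". For the tether, Section 6.6.2 gives three alternative limits: "Tether failure stopping point: 3 of first 5 cases, 5 of first 10, or greater than 50% of cases 15 and beyond". On when a failure can be found, it says: "Diagnosed at any time point after 3 months by increased angulation at a disc space on standing PA radiograph". It then narrows what counts: "Also, it is only an SAE if noted before maturity, overall Cobb angle worsens compared to the first erect measurement, AND requires re-operation". The parallel late limit for procedure-related events in Section 6.6.1 reads "SAE in greater than 50% of patients after 15 cases".

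Section 6.5 gives the consequence: "If any of these rules are met, the study will halt enrollment until appropriate measures can be put in place". Section 3.3.2 plans the study "in up to 40 subjects using the investigational device elements" and says "we may expect to enroll about 5-10 patients per year".

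The plan does not give a minimum follow-up for a case to enter the percentage, a censoring or time-to-event method, a schedule of looks, or an expected failure rate or timing. It also does not say whether a failure found later in one of the first 5 or first 10 cases still counts toward those limits.

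**The concern.** A case implanted last month cannot be a tether failure under the plan's own definition, but on the natural reading it already lowers the percentage. A case implanted a year ago has been watched for only part of the two-year follow-up. Meeting the limit halts enrolment, so the limit matters only while new cases are arriving, which is when this dilution is present. The bias always runs toward not halting and is larger when accrual is faster. Three months is also a minimum delay, because the event counts as serious only once the curve has worsened and re-operation is required.

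At stake is whether the late limit can do its work for an implant in children aged 8-16, in a study whose primary endpoint is safety. The issue is the denominator and arises whatever percentage is chosen.

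**Working it through.** **Plan's own figure.** The documents state no operating characteristics for the stopping rules, so there is none to reproduce. The only computed figure is the paired t-test power in Section 6.4 (above 80% at n = 40). It reproduces as above 0.9999 for both measurements, and it does not bear on this rule.

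**Inputs from the documents.** Limits of 3 of 5, 5 of 10, then more than 50%; diagnosis after 3 months (6.6.2); r = 5 to 10 cases per year and at most 40 cases (3.3.2). On the cumulative reading, the late limit needs 8 of 15 or 21 of 40.

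**Assumptions.** Evenly spaced implants, a look at each implant from case 15 to 40, and the failure rates and timings below.

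**Step 1: dilution.** At the nth implant, case i has been followed for t_i = (n - i) x 12/r months. If F is the distribution of time to a countable failure, then monitored rate / true rate = (1/n) x sum of F(t_i).

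For the 3-month period alone (F = 0 up to 3 months, 1 afterwards):
- 5 per year: spacing is 2.4 months, and the cases at 0 and 2.4 months cannot be assessed. Ratio 13/15 = 0.87 at case 15 and 38/40 = 0.95 at case 40.
- 10 per year: spacing is 1.2 months, and the cases at 0, 1.2 and 2.4 months cannot be assessed. Ratio 12/15 = 0.80 and 37/40 = 0.925.

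| Assumed failure timing | Case 15, 5/yr | Case 15, 10/yr | Case 40, 5/yr | Case 40, 10/yr |
|---|---|---|---|---|
| All visible just after 3 months | 0.87 | 0.80 | 0.95 | 0.925 |
| Even over months 3-12 | 0.76 | 0.55 | 0.91 | 0.83 |
| Even over months 3-24 | 0.59 | 0.27 | 0.85 | 0.71 |

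Later timing lowers the ratio further: even over months 12-24, it is 0.47 and 0.07 at case 15.

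**Step 2: one example.** Assume a true two-year rate of 60%, spread over months 3-24. The expected monitored rate at case 15 is 0.60 x 0.59 = 35% (5/yr) or 0.60 x 0.27 = 16% (10/yr). At case 40 it is 0.60 x 0.85 = 51% or 0.60 x 0.71 = 43%. The chance of exceeding 50% at case 15 is 0.09 or below 0.001, against 0.79 with complete follow-up (binomial, at least 8 of 15). At case 40 it is 0.48 or 0.10, against 0.87.

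**Step 3: all looks, by simulation, same example.**

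| Rule | 5/yr | 10/yr |
|---|---|---|
| Late limit alone, all implanted cases | 69% | 19% |
| Late limit alone, only cases past 3 months | 82% | 38% |
| Early limits (open to later failures) or late limit | 90% | 87% |
| The same, plus a binding Kaplan-Meier limit | about 96% | about 96% |

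With failures over months 3-12 instead, the late limit alone is met in about 84% (5/yr) and 61% (10/yr).

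If the early limits are judged only when the 5th and 10th cases are implanted, they fire in 4% of trials or less at 60% over months 3-24, and the late limit carries almost all the protection. Earlier failures would make them fire more often.

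**Step 4: chance crossings at an assumed true 30%.** The late limit as written: 2% or less. With only cases past 3 months: at most about 5%. A binding Kaplan-Meier limit (at least 5 cases followed to two years): about 7-19%. Early limits open to later failures: about 23%.

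**Step 5: when Kaplan-Meier could operate.** The 5th case reaches 24 months after 24/1.2 = 20 further implants at 10 per year, so at case 25. At 5 per year it does so after 24/2.4 = 10 further implants, at case 15.

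**The case against.** **The denominator is inferred.** A reader might take it that the plan divides by all implanted cases. The text does not say so. The wording could also mean only cases numbered 15 onward. The parallel limit in 6.6.1 favours the cumulative reading, and on the other reading the first looks would be even less mature. The gap stands either way.

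**The size rests on assumed timing.** A reader might infer that the monitored rate reads far below the true one. The one document-based input, the 3-month period, costs only 5-20% in relative terms. Large shortfalls need failures spread over a year or two, and the documents give no timing. This objection stands, so only the direction of the bias is general.

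**The late limit is one of three alternatives.** A reader might infer that a device failing in well over half of cases could easily run to 40 cases without a halt. With the early limits kept open, the whole tether rule already halts in about 87-90% of trials at a true 60%, and adding Kaplan-Meier spares only about 1-2 children on average. This stands only if later failures count toward the early limits, which the plan leaves open.

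**The re-operation limit overlaps.** A tether failure counts as serious only if re-operation is required, and the re-operation limit has the same thresholds without the 3-month start. It therefore covers much of the same ground. It too lacks a follow-up condition, so it shares the dilution from short follow-up.

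**Other oversight exists.** The Safety Officer reviews each event (8.4.1), and progress reports are at least six-monthly for the first 24 months (8.7, 8.8). This lessens the consequence but does not correct the percentage.

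**Conclusion.** The concern holds in a limited form. Followed on its natural reading, the late tether limit understates the eventual failure rate at every look during accrual, and always in the direction of not halting. At 5-10 cases per year the monitored/true ratio at case 15 runs from 0.80-0.87 (3-month period alone) through 0.55-0.76 (months 3-12) to 0.27-0.59 (months 3-24). By case 40 these are 0.925-0.95, 0.83-0.91 and 0.71-0.85.

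The practical loss depends on an unstated point. If later failures count toward the first-5 and first-10 limits, the gain from repairing the late limit is modest. If those limits are read only when the 5th and 10th cases are implanted, the late limit carries most of the protection, and at a true 60% over months 3-24 it is met in only about 19-69% of trials.

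The documents do not support replacing the crude limit with a Kaplan-Meier one. At 10 per year that would leave no late limit before about case 25, and it would raise chance crossings of this limit. All failure rates and timings here are assumptions.

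**What to change.** In Section 6.6.2:

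1. State that the denominator of the late tether limit is all cases implanted so far that have passed the 3-month diagnostic start.
2. State that failures found later in the first 5 and first 10 cases still count toward those limits.
3. Alongside the crude limits, not in place of them, report to the Safety Officer the Kaplan-Meier two-year estimate for tether failure, screw failure and implant re-operation (the last two from Day 0), with the number of cases followed to two years.

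The 50% threshold is unchanged.

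**Cost.** This is a wording change and a short calculation at each look, from dates already collected. Item 1 adds few chance halts (at most about 5% against 2% or less for this limit at a true 30%). Item 2 confirms a reading under which the early limits cross in about 23% of trials at a true 30%, which the sponsor should know. Item 3 is for information only. It needs a stated censoring rule, because subjects withdrawn for adverse events leave study visits and their continued record review needs consent (4.7).

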Safety and Feasibility Evaluations	
We will use phase-specific endpoints to measure safety and feasibility:
 
 1) Study treatment phase: Any individual-level intraoperative events including neuromonitoring events (loss or change in neurological signaling or function), unanticipated events during surgery, and SAEs. 2) Post-operative active phase: Incidence of infection (within 90 days post-op), pneumothorax, bronchopulmonary plug, or any reportable SAE. 3) Extended follow-up phase: Incidence of over-correction, implant failure (measured on serial x-ray), incidence of curve progression to more than 50 degrees at two year follow-up, or incidence of secondary surgery or re-operation to correct further spine deformity (not related to trauma or other issues not related to the initial surgery/disease). Additional follow-up, through two years beyond skeletal maturation, will be conducted by periodic chart review. 4) Feasibility will be assessed by the capacity to successfully implant all components of the anterior vertebral tether device in subjects.
Statistical And Analytic Plan	The enrollment target of 40 subjects for this initial study of the device is based primarily on feasibility rather than statistical concerns. As such, analyses will be primarily descriptive for safety and feasibility. The Cobb angle, the exploratory therapeutic endpoint, will be evaluated as a continuous variable.
Data And Safety Monitoring Plan	The PI and Safety Officer will meet regularly to discuss any safety events. Safety Officer reports will be forwarded to the IRB during continuing review per CHOP Office of Research Compliance monitoring guidance. Safety reporting will be according to IRB

SOP 408 and governing FDA guidelines. The PI and study team will also comply with all CHOP Office of Research Compliance monitoring standards. The PI will meet with the study team regularly to discuss study progress and ensure data fidelity.

TABLE OF STUDY PROCEDURES

Study Phase	Pre-op / Screening	Surgery	Post-Operative Phase				Extended Follow-up Phase		
Visit Number	1	2	N/A	3	4	5	6	7	8
Study Days	Pre-op	0	1-44 (or until discharge)	21 (+/- 21 days)	45 (+/- 21 days)	90 (+/- 21 days)	180 (+/- 90 days)	365 (+/- 90 days)	730 (+/- 90 days)
Clinical Care (SOC) Evaluations:									
All procedures included here are standard-of care for a surgical orthopedic spine patient	X-ray: Hand Bone Age	*							
	X-ray: AP/PA and Lateral Spine	X		*	X	X	X	X	X

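### No procedure-related SAE limit in 6.6.1 counts patients 11 to 14, so the tolerated count climbs from 6/10 to 10/14 before it drops to 7/15

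*Combined protocol and SAP*

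**What the plan says.** Section 6.6.1 lists three limits for SAEs related to the surgery. The earliest looks at five patients: "SAE in all of the first 5 patients or". The next looks at ten: "SAE in 7 of first 10 patients or". The last is open-ended: "SAE in greater than 50% of patients after 15 cases".

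Section 6.6.2 gives one set of numbers for each of three device events (screw, cap or staple failure; tether failure; implant re-operation). Three events among the initial five cases meet the earliest limit. For tether failure, the two later limits are worded as "5 of first 10, or greater than 50% of cases 15 and beyond".

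Section 6.5 states the consequence: "If any of these rules are met, the study will halt enrollment until appropriate measures can be put in place to reduce patient risk". The data and safety monitoring plan in 9.3.1 adds no further limit; the study team will "perform interim safety analyses as outlined in Section 6.6". The synopsis adds that "The PI and Safety Officer will meet regularly to discuss any safety events", without a number attached.

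**The concern.** The procedure-related limits tighten from 100% at 5 patients to 70% at 10 and to more than 50% at about 15. Between the second and third steps nothing is counted. A trial that reaches 6/10 continues, and every one of the next four patients can have a procedure-related SAE without meeting a rule. At 10/14 the rate is above the 70% that would have halted enrolment at case 10, and 8/15 would halt it one case later. The documents give no reason for this rise.

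At stake is how many children are operated on before a prespecified review is forced, in a study whose primary endpoint is safety. At the planned 5 to 10 enrolments per year (section 3.3.2), four cases take 4/10 to 4/5 of a year, about 5 to 10 months.

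The wording of the last limit is a second, separate problem. The phrase in 6.6.1 leaves open whether checking starts at case 15 or case 16. The phrase in 6.6.2 can be read as a rate among cases numbered 15 and above only.

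**Working it through.** **Inputs.** Limits as written in 6.6.1 and 6.6.2; maximum of 40 subjects (6.4). The plan states no operating characteristics for these rules, so there is no figure to reproduce. It also states no procedure-related SAE rate; the true rate p is assumed, from 20% to 60%. Events are taken as independent and known before the next case, and the last limit is taken to start at case 15 over all cases to date.

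**Step 1: tolerated counts (procedure-related).** The highest count at which no rule is met:

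| Cases | 10 | 11 | 12 | 13 | 14 | 15 |
|---|---|---|---|---|---|---|
| As written | 6 (60.0%) | 7 (63.6%) | 8 (66.7%) | 9 (69.2%) | 10 (71.4%) | 7 (46.7%) |

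If checking starts at case 16, 11/15 (73.3%) also continues.

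**Step 2: how often the gap matters.** Let S(n,k) be the probability of k SAEs after n cases with no rule met. Then S(n,k) = p·S(n−1,k−1) + (1−p)·S(n−1,k), set to zero wherever a rule is met. The chance of a running rate above 50% at some point in cases 11 to 14, with no earlier halt, is P(continue past case 10) minus P(continue past case 14 if rates above 50% are removed at cases 11 to 14):

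- p = 30%: 0.988 − 0.910 = 0.078
- p = 50%: 0.822 − 0.443 = 0.379
- p = 60%: 0.611 − 0.193 = 0.418

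The same calculation gives 0.012 at 20% and 0.224 at 40%.

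**Step 3: how much comes from the limit at 10.** Every trial at 6/10 is above 50% at case 11 whatever happens there (6/11 = 54.5%, 7/11 = 63.6%). At p = 40%, P(6/10 with no halt) = C(10,6)·0.4⁶·0.6⁴ − 0.4⁵·(5·0.4·0.6⁴) = 0.1115 − 0.0027 = 0.1088, which is 0.1088/0.224 = 49% of the crossings. The share is 53% at p = 50% and 59% at p = 60%.

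**Step 4: device rules.** From at most 4/10, the tolerated counts are 5/11 (45.5%), 6/12 (50.0%), 7/13 (53.8%) and 8/14 (57.1%). The rate can exceed 50% only at cases 13 and 14, with probability at most about 0.02 for each rule.

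**Step 5: the two denominators.** Take 8 tether failures in 14 cases and none in case 15. Over all cases the rate is 8/15 = 53%, a halt; among cases from 15 on it is 0/1, no halt. Now take 4 in 14 and one in case 15. Over all cases it is 5/15 = 33%, no halt; from case 15 on it is 1/1, a halt. The two readings give opposite decisions.

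**Step 6: effect of a bridge.** Suppose that in cases 11 to 14 enrolment halts when at least 7 patients and more than 50% of all patients to date have a procedure-related SAE. The tolerated counts become 6/10, 6/11, 6/12, 6/13, 7/14 and 7/15. Running the recursion to case 40, the overall halt probability goes from 7.3% to 8.9% at p = 30% and from 33.0% to 35.6% at p = 40%.

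**The case against.** The strongest reply is that a few discrete looks with a falling threshold are a legitimate design. A reader might infer that enrolment continues after the plan's own 50% limit has been passed. The documents do not support that: the limit is not in force before case 15, and the plan openly lets 4/5 (80%) and 6/10 (60%) continue. As step 3 shows, about half or more of the crossings at 40 to 60% are trials that the plan already chose to let run at case 10. This stands, and it limits the point to the boundary rising again after case 10.

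Nor are these patients unmonitored. The PI and Safety Officer meet regularly and judge each SAE (8.4.1). IRB notification is due within 24 hours for deaths and life-threatening events and within 7 days for other SAEs (8.6). A late SAE in patients 1 to 10 can still meet the first-10 rule while patients 11 to 14 are being enrolled. All true, but none of these puts a numerical limit on events in patients 11 to 14.

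The size depends on assumed rates: at 20% the crossing probability is only 1.2%. That also stands.

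Finally, simply checking the 50% limit from case 11 would be incoherent: 6/10 would continue, but an event-free case 11 (6/11) would halt. At p = 40% such halts are 0.1088·0.6/0.224 = 29% of crossings. The bridge in step 6 avoids this, because each of its halts needs a seventh SAE.

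**Conclusion.** The point holds for the procedure-related rules. No limit in 6.6.1 counts patients 11 to 14, and the tolerated proportion rises from 60% to 71% before it falls to 47%. The probability that this matters is 1.2, 7.8, 22.4, 37.9 and 41.8% at assumed true rates of 20, 30, 40, 50 and 60%, partly because 6/10 is allowed. These figures assume independent events that are known at once. A reader might extend the concern equally to the device rules; at no more than about 2% each, the numbers do not support that.

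The difference in wording between 6.6.1 and 6.6.2 needs reconciling whatever the SAE rate. Overall this is a cheap improvement to the safety boundary and does not invalidate the plan.

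**What to change.** In 6.6.1, add one sentence: in cases 11 to 14, enrolment halts when at least 7 patients and more than 50% of all patients to date have had a procedure-related SAE. Both numbers are the plan's own. The tolerated proportion then never rises above the 60% allowed at case 10; from case 12 it only moves between 46% and 50% as whole patients step across one half.

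In both 6.6.1 and 6.6.2, state in the same words that the limit of more than 50% is checked after each case from case 15, with all cases to date as the denominator.

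The cost is two sentences and slightly more enrolment halts, 1.6 percentage points at an assumed 30% (8.9 − 7.3) and 2.6 at 40% (35.6 − 33.0). Under 6.5 a halt lasts only until risk-reducing measures are in place.
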